13 STUDY DESIGN**13.1 DESIGN SUMMARY**

This study will be a clinical safety and effectiveness study of the Biolinq System. The study will be an open label, prospective, multi-center, single arm study conducted in the United States.

13.2 DURATION OF PARTICIPATION

[REDACTED]

13.3 ESTIMATED STUDY DURATION

[REDACTED]

13.4 STUDY CENTERS

A minimum of five (5) and up to eight (8) centers in the United States will participate in the study.

14 STUDY ENROLLMENT**14.1 STRATEGIES FOR RECRUITMENT AND RETENTION**

Subjects will be recruited through various IRB-approved advertising methods including but not limited to digital campaigns, available Investigator treatment databases, print, radio, or the like. All advertising materials will be pre-approved by the reviewing IRB prior to implementation.

[figure not shown]
[figure not shown]
14.2 INFORMED CONSENT

To protect the rights, safety, and welfare of subjects, the study is conducted in accordance with the 21 CFR 50, Protection of Human Subjects. The Principal Investigator or designee, as delegated by Principal Investigator on site delegation of authority log, will explain the study nature, overview, purpose, objectives, expected participation duration, study activities, risks of study participation, alternative treatment, participation benefit, study sponsor, cost for participation, new information sharing, medical cost coverage if he/she gets hurt, stipend amounts, confidentiality, and IRB contact information. Subjects will be given ample time to consider their voluntary participation in the study and to ask questions. Potential subjects may take a copy of the IRB Approved Informed Consent Form (ICF) home to review with family and friends prior to deciding on whether to participate in the study.

[figure not shown]
Participants must be informed that participation is voluntary and that they may withdraw from the study at any time, without prejudice. A copy of the Informed Consent Form will be offered to the participants for their records. The informed consent process will be conducted and documented within the IRB approved Informed Consent Document, with required signatures obtained, before the participant participates in any study activities. The rights and welfare of the participants will be protected by emphasizing to them that the quality of their medical care will not be adversely affected if they decline to participate in this study.

[figure not shown]
14.3 ENROLLMENT

Subjects who sign the IRB approved ICF will be considered “Enrolled” in this study.

14.4 SCREENING**14.5 DEVICE ASSIGNMENT**

15 STUDY PROCEDURES

[figure not shown]

Table 6. Draize Assessment for Erythema and Edema Severity

Value	Erythema	Value	Edema
0	No erythema	0	No edema
1	Very slight erythema (barely perceptible)	1	Very slight edema (barely perceptible)
2	Well-defined erythema	2	Slight edema (edges of area well defined by definite raising)
3	Moderate-to-severe erythema	3	Moderate edema (raised ~ 1 mm)
4	Severe erythema (beet to crimson red)	4	Severe edema (raised more than 1 mm and extending beyond area of exposure)

16 DESCRIPTION OF SAFETY EVALUATION**16.1 DEFINITIONS OF ADVERSE EVENTS (AE)**

An adverse event means any untoward medical occurrence, unintended disease or injury, or untoward clinical signs (including abnormal laboratory findings) in subjects, users or other persons, whether or not related to the BioliniQ MicroArray System. This definition includes events related to the BioliniQ MicroArray System, or the commercially available CGMs as well as events related to the procedures involved. All suspected adverse events will be assessed and monitored by the Principal Investigator, or designee, and recorded in the appropriate source worksheet and transcribed to Case Report Form.

16.1.1 ADVERSE DEVICE EFFECT (ADE)

An adverse device effect is an adverse event related to the use of the BioliniQ MicroArray System.

16.1.2 SERIOUS ADVERSE EVENTS (SAE)

An adverse event (AE) is considered "serious" if, in the view of either the investigator or BioliniQ, it results in any of the following outcomes:

- a) Death
- b) Serious deterioration in the health of the subject, that either resulted in:
 - a. A life-threatening illness or injury, or
 - b. A permanent impairment of a body structure or a body function, or
 - c. In-patient or prolonged hospitalization, or
 - d. Medical or surgical intervention to prevent life-threatening illness or injury or permanent impairment to a body structure or a body function
- c) Led to fetal distress, fetal death or a congenital abnormality or birth defect

16.1.3 UNANTICIPATED ADVERSE DEVICE EFFECT (UADE)

An UADE is not expected to occur; however, an unanticipated adverse device effect (UADE) is defined as any serious adverse effect on health or safety or any life-threatening problem or death caused by – or associated with – the device, if that effect, problem, or death was not previously identified in nature, severity, or degree of incidence in the investigational plan (including documents such as the protocol, the Informed Consent Form, and other study-related documents), or any other unanticipated serious problem associated with the device that relates to the rights, safety, or welfare of subjects.

An Unanticipated Adverse Device Effect (UADE) is a serious adverse device effect that has not been previously identified in nature, severity or degree of incidence in the investigational plan (including documents such as the protocol, the informed consent form, and other study-related documents).

16.2 SEVERITY OF ADVERSE EVENTS

All adverse events will be classified by the Principal Investigator or designee. The following guidelines will be used to describe severity.

- **Mild** – Awareness of signs or symptoms, but easily tolerated; are of minor irritant type; causing no loss of time from normal activities; symptoms would not require medication or a medical evaluation; signs and symptoms are transient.
- **Moderate** – Discomfort severe enough to cause interference with usual activities, requiring treatment but not extended hospitalization or intensive care for the subject.
- **Severe** – Incapacitating, causing inability to do work or usual activities; signs and symptoms may be of systemic nature or require medical evaluation and/or treatment, requiring additional hospitalization or intensive care (prolonged hospitalization).

16.3 RELATIONSHIP OF ADVERSE EVENT TO THE STUDY DEVICE

The Principal Investigator, or designee, will assess all adverse events (AEs) and determine their relation to the Bioliniq MicroArray System. The Principal Investigator, or designee, will use his/her clinical judgment to examine and evaluate the adverse event based on an examination of the subject and the temporal relationship with the use of the device. The degree of certainty about causality will be graded using the categories below.

- **Definitely Related** – There is clear evidence to suggest a causal relationship, and other possible contributing factors can be ruled out. The clinical event occurs in a plausible time relationship to administration of the study device and cannot be explained otherwise.
- **Probably Related** – The AE has a strong temporal relationship to use of the investigational device and another etiology is unlikely.
- **Potentially Related** – The AE has a strong temporal relationship to the use of the investigational device and an alternative etiology is equally or less likely compared to the potential relationship to the investigational device.
- **Unlikely to be related** – The AE has minimum or no temporal relationship to use of the investigational device and/or a more likely alternative etiology exists.
- **Not Related** – The AE is completely independent of the investigational device and is due to an underlying disease state or concomitant medication or therapy not related to the study device.

All device-related irritation will be recorded. Post-removal follow-up may be requested until resolution in the case of any ongoing adverse events.

16.4 ADVERSE EVENT REPORTING

Any AE not considered an SAE, occurring during the study will be documented by the Principal Investigator or designee on the appropriate source worksheet, entered into the Electronic Data Capture system, and reported to the Sponsor within 30 days of the occurrence of the adverse event. All adverse events (mild, moderate, and severe) will be reported in the final Clinical Study Report.

16.4.1 SERIOUS ADVERSE EVENT (SAE) REPORTING

Any SAE, including death, that may occur during a clinical study must be reported immediately (within 24 hours of awareness) to Bioliniq, Inc. Clinical Affairs personnel will document details and Clinical Affairs management's assessment of the SAE in a timely manner. The Sponsor contacts are listed on the protocol title page.

16.4.2 UNANTICIPATED ADVERSE DEVICE EFFECT (UADE) REPORTING

During the review of a reported SAE, if the PI, or designee, determines the severity or extent of the event was not cited in this protocol or the report of prior investigations, and the event was classified as at a minimum, possibly related to the device, the event will be documented as an UADE.

If the event is classified as an UADE, the PI or designee must notify their IRB and Bioliniq will notify the FDA, reviewing IRBs, and other participating Investigators, as applicable, within ten (10) working days of the original SAE notification.

If it is determined that the UADE presents an unreasonable risk to subjects, Bioliniq will terminate all investigations or parts of investigations presenting that risk as soon as possible, but not later than 5 working days after such determination is made and not later than 15 working days after Bioliniq first receives notice of the original SAE. Bioliniq will not resume a terminated study without IRB and FDA approval, as applicable.

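### The UADE rule in Section 16.4.2 gives no stated route for excess incidence or for non-SAE device problems, both covered by the 16.1.3 definition, and its causality threshold is not a grade on the 16.3 scale

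*Combined protocol and SAP*

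**What the plan says.** Three intact parts of Section 16 bear on this.

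**Definition (16.1.3).** The first paragraph covers serious effects, life-threatening problems and deaths that the device causes or is linked to, "if that effect, problem, or death was not previously identified in nature, severity, or degree of incidence in the investigational plan". It then adds a catch-all: "or any other unanticipated serious problem associated with the device that relates to the rights, safety, or welfare of subjects". The material against which an event is judged is described openly, "including documents such as the protocol, the Informed Consent Form, and other study-related documents". A second paragraph restates the definition more briefly: a UADE "is a serious adverse device effect that has not been previously identified in nature, severity or degree of incidence". The restatement has no catch-all.

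**Working rule (16.4.2).** During review of a reported SAE, the event is recorded as a UADE on two conditions. The first is that the PI or a delegate "determines the severity or extent of the event was not cited in this protocol or the report of prior investigations". The second concerns causality: "the event was classified as at a minimum, possibly related to the device". Classification leads to notice to the IRBs, the FDA and other investigators, as applicable, within 10 working days of the SAE notification. If the risk is judged unreasonable, the sponsor must terminate the affected investigations within 5 working days of that judgement and within 15 working days of first notice of the SAE.

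**Causality scale (16.3).** The grades are Definitely, Probably and Potentially Related, Unlikely to be related, and Not Related. Potentially Related reads: "The AE has a strong temporal relationship to the use of the investigational device and an alternative etiology is equally or less likely", compared with a device cause.

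Section 17.2 includes UADEs among the event types counted and summarised by percentage of subjects.

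**The concern.** A definition says what a UADE is, but sites act on the rule that tells them when to record one. Here the two differ. An event can satisfy 16.1.3 while nothing in 16.4.2 directs anyone to classify it. Three things depend on classification: expedited notification, the termination time limits, and the UADE line in the 17.2 safety summary. The threshold is also stated in a word that sites do not record, so the causality grade on the case report form does not say directly whether the condition is met.

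**Working it through.** The plan gives no figure to reproduce, so the check is a comparison of the definition with the rule, element by element.

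1. **Severity.** Named in both. No gap.
2. **Incidence.** An explicit ground in 16.1.3, not named in 16.4.2. Extent is undefined and covers frequency only on a generous reading. A serious effect already described, at a severity already described, but occurring more often than previously identified meets 16.1.3 and does not clearly meet 16.4.2.
3. **Other unanticipated serious problems.** In the first paragraph of 16.1.3, absent from 16.4.2. The rule begins with a reported SAE, and 16.1.2 limits SAEs to listed outcomes. A serious device problem without such an outcome goes elsewhere: if it is an AE, to the sponsor within 30 days (16.4); if it is a device inadequacy, to the sponsor as a Device Observation (16.5), with no deadline stated. Neither section mentions a UADE check.
4. **Time limits.** The 10-day and 15-day limits both count from the SAE notice. For an event never logged as an SAE, neither has a start date. The 5-day limit counts from the finding of unreasonable risk and is not affected.
5. **Causality.** Possibly related matches none of the five grades. The only grade between Probably and Unlikely is Potentially, which requires a strong temporal relationship. Unlikely requires little or no temporal relationship, or a more likely alternative cause, or both. An event with a moderate temporal relationship and no more likely alternative fits neither description, and there the undefined word would matter most.
6. **Nature.** Named in 16.1.3 but not in 16.4.2. If a kind of event appears nowhere in the cited documents, its severity is not cited either, so the rule already catches it. This is a difference of wording.
7. **Reference documents.** 16.4.2 names the protocol and the report of prior investigations. The list in 16.1.3 is open-ended and includes the consent form. An event disclosed only in the consent form would be unanticipated under 16.4.2 but anticipated under 16.1.3. On this element the rule can be the wider of the two.

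**Why incidence needs study-wide data.** The synopsis plans at least 206 treated subjects at 5 to 8 centers. Assuming equal enrolment, 206/8 = 25.75 and 206/5 = 41.2, or about 26 to 41 subjects per site. One PI sees only that fraction.

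**The case against.** The best defence is that 16.4.2 says if, not only if. Notification is tied to an event being classified as a UADE, and 16.1.3 still defines the term, so a careful site or sponsor could classify an event directly from the definition. This stands in part: nothing forbids that route. But no text sets it out or assigns it to anyone, and the 10- and 15-day limits would still lack a start date for a non-SAE event.

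Several stronger readings are tempting, and the documents do not support them.

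- *Events of a new kind are excluded.* They are not, in practice: an event cited nowhere has no cited severity either.
- *The shorter document list narrows the rule.* Naming fewer documents makes fewer events anticipated, so it can widen the rule.
- *One site's PI decides and the sponsor has no view.* Under 16.4.1 every SAE reaches the sponsor within 24 hours and Clinical Affairs management's assessment is documented. Under 16.1.2 the sponsor may itself judge an event serious. Section 24 makes the sponsor responsible for informing IRBs and the FDA, if applicable, of significant new information. What is missing is an explicit UADE step, not study-wide visibility.
- *The causality wording shuts events out.* Possibly is most likely a slip for Potentially, and few readers would take Unlikely to satisfy it. The threshold is undefined; that is not evidence that sites will differ.
- *Events disappear from the safety data.* They do not. All AEs go into the final report (16.4) and a by-subject listing (17.2). Device Observations (16.5) and deviation reporting (21.1.1) are further routes. The UADE label and the expedited notice are what may be lost.

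Section 19.1 lists 21 CFR Part 812 among the regulations. It may supply obligations that 16.4.2 omits, but its text is not in these documents and a site following the protocol would not see it.

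**Conclusion.** The concern holds as an internal conflict in a safety rule. Two groups of events can meet 16.1.3 without a stated route through 16.4.2: known serious device effects at excess incidence, and serious device problems that are not SAEs. Separately, the causality threshold is not on the recorded scale.

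The number of events at stake cannot be estimated. The device-risk section is redacted in the public copy and the report of prior investigations is a separate document, so the previously identified incidence is not visible. Section 16.1.3 itself expects no UADE, which suggests few. No effectiveness endpoint or estimate depends on the point. It should still be corrected, because it bears on expedited safety notification and the reported UADE count and costs almost nothing to repair.

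The conclusion rests on reading 16.4.2 as the text sites will act on, and on extent not being defined to include frequency in any part not shown. The intact UADE text gives no sign of such a definition.

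**What to change.** Reconcile 16.1.3, 16.3 and 16.4.2:

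- In 16.4.2, replace the severity-or-extent test with a cross-reference to the full first-paragraph definition in 16.1.3, including incidence and the catch-all.
- Align the reference documents in 16.4.2, and the second paragraph of 16.1.3, with that definition.
- Start the 10- and 15-working-day limits from the sponsor's first notice of the event, whether or not it was logged as an SAE.
- State the causality threshold as a named grade on the 16.3 scale.
- Add that the sponsor's existing SAE assessment in 16.4.1 includes a check against the UADE definition, with incidence judged on study-wide data.

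The cost is a protocol wording change and one added check within an assessment the sponsor already documents. The possible downside is a few more events classed as UADEs.

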16.5 DEVICE OBSERVATION REPORTING

A Device Observation (DO) is defined as any suspected inadequacy in the identity, quality, durability, reliability, safety or performance of an investigational device, including malfunction, misuse or use errors, or inadequacy in information supplied by the Sponsor.

Site will document Device Observations on source documents and CRFs at each occurrence and notify sponsor. All applicable DOs will be recorded on the Investigational Product Accountability log.

17 STATISTICAL ANALYSIS & METHODS

17.1 ANALYSIS COHORTS

Analysis cohorts for the study are prospectively defined and are described in the following subsections. To ensure that the calculated percentage of points is representative across all glucose ranges (i.e. data from each of the glucose range should be adequately represented and not heavily weighted toward the midrange at the expense of the high and low range glucose values), glucose levels will be manipulated during the in-clinic sessions (Table 5).

Information pertaining to the statistical analysis methods using these cohorts is provided in the subsequent sections.

17.1.1 ENROLLED COHORT

The Enrolled Cohort includes all subjects who sign the study IRB approved informed consent. Analyses pertaining to screening eligibility, safety, and protocol compliance prior to the Bioliniq application, and study exit will be performed using the Enrolled Cohort.

17.1.2 TREATED COHORT (ANALYSIS POPULATION)

All enrolled subjects who have undergone device application will be included in all analyses. All data that is collected during the study will be included in the analysis.

[figure not shown]
17.2 STATISTICAL METHODS FOR SAFETY OUTCOME

[figure not shown]
Overall and individual adverse events are summarized for safety outcome by frequency and percentage. In addition, the number of AEs, ADEs, SAEs, SADEs, and UADE and percentage of Subjects with events are summarized. A by-Subject listing of adverse events will also be provided in the study report.

[figure not shown]
The erythema and edema Draize assessment at each biowearable wear location is another safety outcome that will be analyzed and reported. [REDACTED]

s.

[figure not shown]
17.3 METHOD DEFINITIONS FOR PERFORMANCE METRICS

DCO-2025-0014

18 DATA MANAGEMENT PLAN

18.1 CASE REPORT FORMS (CRFS)

Investigators are responsible for delegating personnel to complete the appropriate case report forms for each subject enrolled in the study. The CRFs should be completed within 5 working days of study visit or the day data is received. The Investigator must sign for data accuracy and completeness contained on each CRF. BioliniQ will provide training and instructions to each investigational site on how to properly complete these CRFs.

18.2 SOURCE DOCUMENTS

Source documents refer to the records on which clinical observations are first recorded. Original source documentation must be maintained at the investigational site to substantiate data entered on the CRFs. Source documentation must be made available by the investigational site so that information entered on CRFs is verified

and facilitates monitoring by Biolinq or its authorized representative. Source documents must also be made available to any regulatory agency in the event of an inspection so that the integrity of study data may be verified.

The Sponsor will provide sample source worksheets to help with the collection of information for transfer to the EDC System. Sample source worksheets may be revised by site to match workflow or site requirements provided that all required data is collected. In cases where no original source data otherwise exists, a source document worksheet provided by the site or sponsor may be used to establish a source record. To minimize data-related errors, considerations should be taken to avoid duplicative generation of source documentation. All source documents must be signed and dated by the qualified individual generating the record and/or investigator when applicable.

18.3 DATA MANAGEMENT

A 21 CFR Part 11 compliant electronic data capture (EDC) system will be used for data collection in the study. User Acceptance Testing will be performed to validate each eCRFs utilized in the study prior to its use and all subsequent updates. Data is entered into the EDC system by trained delegated personnel as indicated on the Delegation of Responsibilities Log and on its appropriate electronic case report forms (eCRFs). The eCRFs must be completed or updated to reflect the latest data on each Subject participating in the study. The Investigator or authorized Sub-investigator electronically signs the eCRFs testifying data entry accuracy and completeness.

[figure not shown]
No study document should be destroyed without prior written agreement between Biolinq and the investigational site. If an investigational site is no longer enrolling Subjects or following any enrolled Subjects, an investigator may transfer custody of study records to Biolinq providing a notice of such transfer is given within 10 working days.

The investigational site must maintain study documentation on paper or electronic file for each Subject file. If additional study documentation is required for submission to Biolinq, it must be redacted to remove the Subject's name or other Subject identification, and the Subject's unique identification code inserted prior to being sent to Biolinq.

In the Subject file, information should include corresponding follow-up dates, data noted on Table 8, and reasons for early withdrawal from the study if applicable or study exit after activity completion per protocol. It must be possible to verify subject consent to participate in the study, inclusion, and exclusion criteria in the study from the Subject file. These documents should identify the Subject. Evaluation of these records should be documented as necessary, signed, and dated by the Investigator. All data recorded on the eCRFs must be in the Subject's source data.

